SYNOPSIS

PROTOCOL AnticipUSC – N°ICO 2016-A-04

A) Clinical Trial Identification

TITLE OF THE TRIAL: *Multicenter, open-label, randomized study comparing early postoperative prophylactic non-invasive ventilation in the intensive care unit versus standard postoperative follow-up in patients at high risk of postoperative pulmonary complications according to the preoperative ARISCAT score, undergoing surgery under general or regional anesthesia (ANTICIPUSC)*

SHORT TITLE: ANTICIPUSC

COORDINATOR: [name] [name]

ESTIMATED NUMBER OF CENTERS: 3

NUMBER OF PATIENTS: 266

B) Sponsor Identification

NAME OF THE ORGANIZATION: ICO, DRCI-Cellule de Promotion

CONTACT PERSON: MME [name]

[contact]

[contact]

C) General Information About the Trial

Indication:

This study will focus on a selected population at high risk of postoperative pulmonary complications (PPC) according to the ARISCAT score, among all surgical patients in the participating centers, whether undergoing surgery under General Anesthesia (GA) or Regional Anesthesia (RA), who may benefit from preventive postoperative management.

Primary objective:

The primary objective of the study is to compare the effectiveness of a preventive postoperative management strategy using non-invasive ventilation (NIV) in the intensive care unit versus standard care, on the incidence of acute respiratory failure within 7 postoperative days during hospitalization, in patients at high risk according to the ARISCAT score.

Secondary objectives:

- The safety and tolerability of the strategy under study
- The cause of acute respiratory failure (arf) among the different postoperative pulmonary complications (ppc)
- Mortality during hospitalization for surgery, up to a maximum of 7 days
- Any effect on patient reintubation (cause and timing)
- Any effect on the length of stay in the icu/intensive care unit and on invasive or non-invasive mechanical ventilation
- Any effect on the incidence of healthcare-associated infections, defined according to the centers for disease control (cdc) criteria.

Inclusion criteria:

1. Patient aged 18 years or older
2. Patient scheduled for elective surgery or considered semi-urgent (pre-anesthesia consultation < 48 hours before the surgical procedure), under General Anesthesia (GA) or Regional Anesthesia (RA)
3. Patient with an ARISCAT score greater than or equal to 45 (high risk of PPC)
4. Written informed consent signed by the patient

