5. Patient affiliated with a social security system

Exclusion criteria:

1. Minors, pregnant or breastfeeding women
2. Obstetric procedures
3. Surgeries under Local Anesthesia (LA) or peripheral nerve block
4. Procedures performed outside an interventional room (e.g., operating theater or interventional radiology)
5. Procedures related to previous surgical complications
6. Patients reoperated during follow-up (no double inclusion for the second surgery)
7. Organ transplantation
8. Patients already intubated preoperatively
9. Outpatient surgery
10. Refusal to participate or inability to provide informed consent
11. Persons deprived of liberty or adults under guardianship
12. Participation in another interventional study.

Primary endpoint:

Occurrence of acute respiratory failure (ARF) within 7 postoperative days during hospitalization, validated by the blinded adjudication committee with respect to the randomization arm.

Secondary endpoints:

Assessment of the safety and tolerability of the strategy under study:

- Discomfort or intolerance to NIV, defined as the inability to achieve the target of 6 to 8 hours per day due to premature termination of sessions caused by intolerance, despite proper implementation of NIV, including excessive leaks when these are the reason for stopping sessions
- Skin lesions at contact points between the interface and the patient's skin
- Anastomotic suture dehiscence (digestive or bronchial) when caused by a total pressure (PEEP + IPAP) > 20 cmH₂O
- Gastric distension defined as aeric distension of the gastric air pocket evidenced by imaging or gastric tube aspiration
- Occurrence of aspiration of secretions or vomit whose evacuation was hindered by the NIV mask

Any ARF must lead to investigation of its etiology using appropriate examinations:

Infectious pneumonia defined by a Modified Clinical Pulmonary Infection Score (CPIS) > 6, with microbiological thresholds of culture concentrations >10³ CFU/ml for a protected distal sample, >10⁴ CFU/ml for bronchoalveolar lavage, and >10⁶ CFU/ml for tracheal aspiration

The Modified Clinical Pulmonary Infection Score (modified CPIS)

CPIS Points	0	1	2
Tracheal secretions	Rare	Abundant	Abundant + purulent
Chest X-ray infiltrates	No infiltrate	Diffused	Localized
Temperature, °C	≥36.5 and ≤38.4	≥38.5. and ≤38.9	≥39 or ≤36.4
Leukocytes count, per mm ³	≥4,000 and ≤11,000	<4,000 or >11,000	<4,000 or >11,000 + band forms ≥500

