
- Death from any cause during hospitalization for surgery

Assessment of an effect on patient reintubation:

- Reintubation due to respiratory failure (ARF)
- Reintubation due to non-respiratory failure, excluding reintubations specifically for a new surgical or interventional radiology procedure
- Time to reintubation to assess delayed reintubation (characterized by a non-significant difference in reintubation rate between groups but a longer delay in the NIV group)

Assessment of an effect on length of stay in ICU and duration of invasive or non-invasive mechanical ventilation:

- Number of days of invasive mechanical ventilation (intubated or tracheostomized) during hospitalization for surgery, including episodes of reintubation
- Number of days of non-invasive mechanical ventilation (NIV) during hospitalization for surgery, including prophylactic and therapeutic NIV.

**Assessment of an effect on the incidence of healthcare-associated infections, defined according to
Centers for Disease Control (CDC) criteria:**

- Infectious pneumonia: see secondary endpoint criteria
- Urinary tract infection: fever $> 38^{\circ}\text{C}$ and urine culture showing no more than two microbial species, at least one with a concentration $> 10^5 \text{ CFU/ml}$, in a patient with no other obvious source of infection
- Catheter-related infection: fever $> 38^{\circ}\text{C}$, positive catheter culture or sample, and resolution of fever within 48 hours after catheter removal without antibiotic change and no other identified source of infection
- Bacteremia: fever $> 38^{\circ}\text{C}$ and at least one positive blood culture (two or more if coagulase-negative staphylococcus)
- Surgical site infection

Data collection is performed prospectively throughout the first 7 days of hospitalization for surgery.

D) Description of Investigational Medicinal Products

MEDICAMENTS :

Name of the Medicinal Product (INN)	Brand Name	Pharmaceutical Form	Route of Administration	Dosage per Administration
Medical Liquid Oxygen	N/A	Gas	N/A	

Therapeutic regimen:

The ventilatory mode used will be an assisted mode (PSV or BiPAP), as these have shown a stronger (86) and more sustained effect (29) than CPAP alone.

The interface—nasal mask, face mask, or helmet—is chosen according to the unit's usual practice.

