Statistical analyses will be performed using R software and IBM SPSS.

A total of 266 patients are planned for inclusion, divided into two balanced groups.

DESCRIPTION OF PLANNED STATISTICAL METHODS:

Research Protocol

Patients will be analyzed on an intention-to-treat basis and then per-protocol.

Intention-to-treat analysis: all patients included in the study for whom outcome data are available will be considered in the analysis according to their randomization group. No imputation method will be used in case of missing data.

If organizational constraints prevent the patient from receiving prophylactic NIV (despite inclusion in the corresponding intervention arm), the patient will remain in their randomization arm for the entire study duration, and their data will be analyzed on an intention-to-treat basis.

Per-protocol analysis excludes patients for whom the initial protocol was not fully adhered to. Only patients who followed the protocol will be considered in the analyses, within the arm to which they were originally randomized.

The analysis will focus on the primary endpoint to determine whether randomization to the "PPC prevention strategy" arm leads to a reduction in PPC frequency compared to the control group. Effect size and number needed to treat will be calculated.

Similarly, for secondary endpoints, significant differences between the two groups will be sought in terms of:

- a) Safety and tolerability of the strategy under study (see safety assessment parameters)
- b) Mortality during hospitalization
- c) Patient reintubation
- d) Length of stay and duration of invasive or non-invasive mechanical ventilation

Description of the overall analysis method

The significance threshold is set at 0.05, and all tests will be two-sided. For qualitative variables, results will be reported as counts and percentages. For quantitative variables, results will be reported as means and standard deviations in case of normal distribution, and as medians with 25th and 75th percentiles in the absence of a Gaussian distribution. Normality of continuous variables will be assessed using the Kolmogorov-Smirnov test.

A simple descriptive analysis will be performed on the entire study population and by subgroups. This description will include sociodemographic data, medical history, ongoing treatments, etc.

A qualitative and quantitative analysis of missing data will be performed. No imputation of missing data is planned for the endpoints.

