- Identification of factors associated with failure of prophylactic NIV in the subgroup where NIV was prematurely discontinued.

Statistical Justification for Sample Size:

Previously described data indicate that the expected effect size is approximately a 50% reduction in events:

- In studies on medical populations, the effect of prophylactic NIV was observed even on harder endpoints than ours: -66% reduction in reintubation, -51% reduction in ARF incidence, and -50% reduction in reintubations, and again -69% reduction in ARF incidence.

- In surgical populations, prophylactic NIV has led to a reduction in restrictive syndrome of about 50%, an improvement in pulmonary function tests (PFTs) of +30%, and a decrease in length of stay by 7 days.
- In curative use after abdominal surgery—a more unfavorable situation since ARF is more advanced—Squadrone reported favorable outcomes in 90% of cases with CPAP, and reintubations were reduced by 30%.

Given that the expected incidence of ARF in the high-risk group is 30–50%, a sample size of at least 121 subjects per arm is required to demonstrate, under a two-sided hypothesis, a relative reduction of 50% in ARF between a group managed with prophylactic NIV (15%) and a group managed with standard care (30%), with an alpha risk of 5% and a beta power of 90%. We anticipate 10% of patients will be non-evaluable.

The required sample size is therefore $242 + 24 = 266$ high-risk subjects evaluated for PPC.

STATISTICAL STOPPING RULES:

No interim analysis is planned in the protocol. However, if during the review of safety and efficacy data provided to the independent monitoring committee (raw, descriptive, and summarized data without pre-established statistics by the investigator or sponsor), a highly significant difference is identified for the primary endpoint or one of the safety parameters when comparing the two groups blinded to treatment allocation, the committee may decide to stop the study.

METHOD FOR HANDLING MISSING, UNUSED, OR INVALID DATA:

Patients included in the study for whom an endpoint is not available will not be considered in the analysis for that missing endpoint. No imputation method will be used for missing data.

MANAGEMENT OF CHANGES TO THE INITIAL ANALYSIS PLAN:

Modifications to the initial analysis plan may be proposed by the monitoring committee (interim analysis, statistical tests, adverse events, secondary objectives) if new literature data justify them.

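### Stopping for harm rests on the same undirected, allocation-blinded, highly significant difference as stopping for benefit, and the synopsis does not name death or reintubation as harm outcomes

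*Combined protocol and SAP*

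**What the plan says.** Section E, under the statistical stopping rules, plans no interim analysis. It then allows the independent committee, which receives safety and efficacy data without prepared statistics, to stop if "a highly significant difference is identified for the primary endpoint or one of the safety parameters when comparing the two groups blinded to treatment allocation". Its wording is permissive: the committee may stop. No p-value, direction or timetable is given.

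The synopsis does not define the safety parameters. The nearest pointer is item a) of the planned comparisons in section E, "Safety and tolerability of the strategy under study (see safety assessment parameters", where mortality and reintubation follow as separate items b) and c). The secondary objectives in section C likewise list safety and tolerability separately from "Mortality during hospitalization for surgery, up to a maximum of 7 days" and from reintubation.

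The safety and tolerability endpoints in section C are five:
- "Discomfort or intolerance to NIV, defined as the inability to achieve the target of 6 to 8 hours per day"
- "Skin lesions at contact points between the interface" and the patient's skin
- anastomotic dehiscence caused by excess pressure
- gastric distension
- aspiration hindered by the mask

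Mortality ("Death from any cause during hospitalization for surgery") and reintubation appear under their own headings. Reintubation covers respiratory and non-respiratory failure, "excluding reintubations specifically for a new surgical or interventional radiology procedure". Time to reintubation is included to look for a delay, characterized by a "non-significant difference in reintubation rate between groups but a longer delay in the NIV group".

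**The concern.** A harm rule and a benefit rule have different jobs. Stopping early for benefit should need strong evidence. Stopping for harm normally should not, because waiting for strong evidence means exposing more patients. Here one high bar covers both, and the comparison is to be made without knowing which group received NIV, so on the written rule the committee would not know whether a difference favours NIV or counts against it.

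The outcomes on which most readers would judge harm from prophylactic NIV are death and reintubation, including reintubation that NIV has only postponed. The synopsis names neither as a trigger. Meanwhile two of the five listed items, intolerance and mask skin lesions, should differ between arms largely because only one arm is assigned NIV. At stake is whether the plan's only written stopping guidance helps the committee recognise harm.

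**Working it through.** **Inputs.** The plan has 266 patients allocated 1:1, so 133 per arm; half recruitment is taken as 66 per arm. Acute respiratory failure (ARF) of 30% in control and 15% with NIV comes from the sample size section. All other rates are assumptions, because the plan gives none: death 3% in control, reintubation 10% in control, and an ARF harm case of 45% with NIV. The high-significance standard is read as two-sided Fisher p<0.01, also an assumption; p<0.001 is in brackets. The rule states no figure of its own to reproduce.

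**Formula.** With n per arm and true rates p_C and p_N, the probability of meeting the criterion is the sum over all counts (x_C, x_N) of Bin(x_C; n, p_C) × Bin(x_N; n, p_N), keeping only pairs whose Fisher p is below the threshold.

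**Counts needed at 66 per arm.** With 2 control deaths (3% of 66), 11 NIV deaths give p=0.016 and 12 give p=0.0088, so 12 are needed. With 7 control reintubations (10% of 66), 19 give p=0.015 and 20 give p=0.0088, so 20 are needed.

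**Probability of meeting the criterion.**

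| Comparison (control vs NIV) | 66 per arm | 133 per arm |
|---|---|---|
| Death 3% vs 6% | 0.008 (0.0003) | 0.035 (0.006) |
| Death 3% vs 9% | 0.056 (0.005) | 0.21 (0.07) |
| Reintubation 10% vs 20% | 0.11 (0.025) | 0.33 (0.12) |
| ARF benefit, 30% vs 15% | 0.24 (0.07) | 0.59 (0.31) |
| ARF harm, 30% vs 45% | 0.17 (0.05) | 0.43 (0.19) |

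The half-recruitment column matters most, because stopping protects patients only while some remain to be recruited.

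**How much is the wording and how much the sample size.** At p<0.05 and 66 per arm, death 3% vs 6% is met with probability 0.04, death 3% vs 9% with 0.17, and reintubation 10% vs 20% with 0.28. For death, a looser conventional threshold helps little; for reintubation it helps more.

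**Direction.** The two ARF rows give similar trigger probabilities but call for opposite judgements. With groups labelled only A and B, the data look the same in kind.

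**Delayed reintubation.** The plan characterizes it by a non-significant difference in rate, so a highly significant difference in rate cannot flag it. This follows from the definition and needs no calculation. Recognising it also requires knowing which group is NIV.

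**Intolerance.** Against 0 in control at 66 per arm, 8 cases reach p<0.01 (p=0.0062; 7 give 0.013). The criterion is met with probability 0.017 (0.0004) at a true rate of 5%, 0.34 (0.06) at 10% and 0.97 (0.79) at 20%. If curative NIV in control also counted, 20% vs 6% (20% of a 30% ARF rate, all treated with NIV) gives 0.35 (0.11). The same 20% vs 6% case applies to mask skin lesions.

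**The case against.** The case on the other side is substantial, and several parts of it stand.

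- *The safety parameters may be defined elsewhere.* This stands. A reader might infer that the rule excludes death and reintubation, or steers the committee away from them. The document is a synopsis with no committee charter or full safety section, so it supports only that they are not named here.
- *The insensitivity is sample size, not wording.* This largely stands for death, as the p<0.05 figures show. But it argues against any significance requirement for harm, rather than for keeping a strict one.
- *NIV-specific items would reveal the arm, so direction is visible in practice.* Probably so. Then the blinding protects little and costs little to give up. If it is real, direction is lost.
- *Delayed reintubation describes a secondary endpoint and is not a trigger.* This stands. The point is true by definition, and with few reintubations no test would detect a delay reliably. Displaying times by arm informs the committee; it does not create power.
- *An independent committee would not stop over mask intolerance.* A reader might infer that the trial would be stopped for it. The rule says only that the committee may stop, the documents give no intolerance rate, and the control rate may not be zero. This remains a secondary clarification.
- *The rule is discretionary, the committee sees the data, and ARF already captures some reintubations.* All true, and these limit the consequence. ARF does not cover non-respiratory reintubation or deaths from other causes.

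**Conclusion.** The concern holds in a limited form. The only written stopping guidance sets one undirected, blinded, high-significance bar for benefit and harm, and in this synopsis it does not name death or reintubation as harm outcomes. On that reading a doubling of death would meet the bar at half recruitment with probability 0.008, and a doubling of reintubation with probability 0.11. These figures rest on p<0.01 as the meaning of the standard and on assumed base rates of 3% and 10%; p<0.001 makes them lower.

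It does not follow that the committee is prevented from acting on deaths, and no final estimate or error rate is shown to change. The consequence is minor to moderate. The change is still worth making, because it concerns patient safety and is nearly free. The intolerance point matters only if the rate is about 10% or more with NIV and near zero in control.

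**What to change.** Amend the stopping sentence in section E:

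1. Name all-cause death, and reintubation for ARF or non-respiratory failure (not for a new procedure), as the outcomes on which harm is judged, with time to reintubation shown by arm. State that stopping for harm does not require a highly significant difference.
2. Give the arm identities to the committee and to no one else, so that every comparison, including ARF, is read with its direction.
3. As a secondary clarification, state that a between-arm difference in NIV intolerance or mask skin lesions is not by itself a reason to stop. Dehiscence, gastric distension and mask-related aspiration stay under review as harms.

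Optionally, a one-sided Fisher p<0.10 against NIV for death or reintubation at half recruitment prompts a documented discussion, not a stop. At 66 per arm it fires with probability 0.16 for death 3% vs 6% (with 2 control deaths, 7 in the NIV arm are needed) and 0.53 for reintubation 10% vs 20%. With no true difference it fires with probability 0.023 and 0.055 respectively. It remains weak for death.

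The cost is about three sentences; the committee and its data already exist. The downside is that the committee is no longer formally blinded, which loses little in an open-label trial, and that harm rests on its judgement instead of a fixed threshold.

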Protocol deviations will be identified and measured. Dual analysis—intention-to-treat and per-protocol—will assess the impact of protocol deviations on study results.

SELECTION OF PATIENTS FOR ANALYSIS:

All patients included in the study, meeting all inclusion criteria and presenting no exclusion criteria, will be included in the analyses of available endpoints according to their case report forms.

See Criteria for Premature Discontinuation of a Participant's Involvement in the Study:

- **Withdrawal of consent:** Data collected will not be included in the intention-to-treat analysis.
- **Discontinuation by the investigator:** Data already collected will be used in the analyses unless the subject withdraws consent.
- **Lost to follow-up:** Data collected for subjects lost to follow-up will be used in the analyses unless the subject withdraws consent.
- **Organizational impossibility to receive prophylactic NIV (inclusion in the corresponding intervention arm):** The patient will be included in the intention-to-treat analysis and followed under the same conditions as in the control arm.

RANDOMIZATION

High-risk patients with an ARISCAT score ≥ 45 will be randomized upon inclusion in the study during the preoperative period (consultation or pre-anesthesia visit, and no later than the day of surgery before anesthesia begins).

Treatment allocation will be performed through centralized computerized electronic randomization by minimization into two groups (1:1), with stratification by center, sex, age, preoperative SpO₂, presence of respiratory infection within the previous month, anemia, surgical incision (upper abdominal or intrathoracic), expected surgery duration (≤ 2 h, 2–3h, > 3 h), and procedure urgency.

F) Planned Duration of the Trial

Inclusion period:	30 months
Treatment period:	48 hours
Follow-up period:	7 days
Total duration of the trial (including follow-up):	30.5 months

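### The intention-to-treat rule drops ARF outcomes already observed in patients who withdraw consent, and no planned analysis tests the result against missing ARF; the bias is probably small and of unknown direction

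*Combined protocol and SAP*

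**What the plan says.** All places are in section E of the combined protocol and SAP.

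- **Description of planned statistical methods** defines intention to treat: "all patients included in the study for whom outcome data are available will be considered in the analysis according to their randomization group". There is no imputation.
- **Selection of patients for analysis** sets a different rule for withdrawal of consent: "Data collected will not be included in the intention-to-treat analysis". The bullet on loss to follow-up repeats the exception: "Data collected for subjects lost to follow-up will be used in the analyses unless the subject withdraws consent". The bullet on discontinuation by the investigator is worded to the same effect. Patients who cannot be given NIV for organisational reasons stay in the intention-to-treat analysis.
- **Method for handling missing, unused, or invalid data** makes the analysis available-case: "Patients included in the study for whom an endpoint is not available will not be considered in the analysis for that missing endpoint".
- **Description of the overall analysis method** adds: "A qualitative and quantitative analysis of missing data will be performed". It does not say that the treatment effect will be re-estimated under other assumptions about the missing outcomes.
- **Statistical justification for sample size** allows for loss: "We anticipate 10% of patients will be non-evaluable". It gives no figure for withdrawal of consent alone.

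**The concern.** A patient whose ARF has been recorded has outcome data and belongs in the analysis under the first definition, yet leaves it under the second if consent is later withdrawn. The two statements disagree about who is in the primary analysis. The second also discards observed outcomes for a reason that arises after randomisation.

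The trial is open-label and only one arm is assigned hours of mask ventilation each day, so withdrawal could depend on arm and on respiratory state. If patients in respiratory difficulty withdraw from the NIV arm, NIV looks better than it is. If comfortable patients who dislike the mask withdraw, it looks worse. Blinded adjudication protects the classification of ARF but cannot restore a deleted patient. The planned description of missing data would show how many outcomes are absent, not whether the conclusion depends on them. The paired intention-to-treat and per-protocol analyses are aimed at protocol deviations, and neither brings back data from patients who withdrew consent.

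**Working it through.** **Inputs from the plan.** ARF 30% under standard care and 15% with NIV; two-sided alpha 0.05; 121 evaluable patients per arm; 24 added for non-evaluable patients. 242 + 24 = 266, so 133 per arm with 12 non-evaluable in each. (The usual pooled formula for two proportions gives 121 per arm at 80% power and 161 at the stated 90%. That is a separate matter; 121 is used here only as the planned evaluable number.)

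**Assumptions.** The share withdrawn, w, and the ratio of ARF risk in those who withdraw, m, are not in the documents, so ranges are shown. Tests are Pearson chi-square without continuity correction.

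**1. Shift in the risk difference at the design rates.** If a share f of an arm with true risk r is deleted, and the deleted patients have risk q, the remaining risk is (r − f·q)/(1 − f). Take the same f in both arms.

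- NIV q = 30% (twice 15%), control q = 30%, f = 2%: (0.15 − 0.006)/0.98 = 0.147, a shift of −0.3 points.
- f = 5%: (0.15 − 0.015)/0.95 = 0.142, a shift of −0.8 points.
- f = 10%: (0.15 − 0.03)/0.90 = 0.133, a shift of −1.7 points.
- Other direction, f = 10%, control q = 60%, NIV q = 15%: control becomes (0.30 − 0.06)/0.90 = 0.267, a shift of +3.3 points against NIV.

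The design effect is 15 points.

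**2. Type I error with no true effect (30% in both arms).** Withdrawal is from the NIV arm only, leaving 130, 126 or 120 patients at w = 2%, 5% or 10%, against 133 controls. The remaining NIV risk is 0.30/(wm + 1 − w) if m is relative to those who stay, or 0.30(1 − wm)/(1 − w) if m is relative to the whole arm. Rejection probabilities come from exact binomial enumeration.

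| Withdrawn (NIV / control) | m | Two-sided type I error |
|---|---|---|
| 0 / 0 | – | 5.1% |
| 2% / 0 | 2 | 5.2% |
| 5% / 0 | 2 | 5.7-5.9% |
| 10% / 0 | 2 | 7.7-9.1% |
| 10% / 0 | 0.5 | 5.7-5.8% |
| 5% / 2% | 2 | 5.3-5.4% |
| 10% / 5% | 2 | 5.6-6.1% |
| 5% / 5% | 2 | 5.0% |

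The chance of a false NIV benefit alone, 2.6% with no withdrawal, is 2.8-8.6% over w = 2-10% for m = 1.5-2, and 1.3-2.2% for m = 0.5.

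**3. Tipping points.** The planned result is 18/121 vs 36/121, p = 0.0055. Suppose ARF status is missing for 12 patients per arm. The table gives the number of ARF cases among the 12 missing NIV patients at which p first reaches 0.05 or more.

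| ARF among 12 missing controls | Planned, 18/121 vs 36/121 | Borderline, 22/121 vs 36/121 (p = 0.035) | p at that count |
|---|---|---|---|
| 2 | 7 | 3 | 0.061 |
| 4 | 9 | 5 | 0.066 |
| 6 | 10 | 6 | 0.051 |
| 8 | 12 | 8 | 0.055 |

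For example, 4 control and 9 NIV cases give 27/133 vs 40/133, p = 0.066; with 8 NIV cases, 26/133 vs 40/133, p = 0.047. At the extreme bound for the planned result (every missing NIV patient has ARF, no missing control does), 3 missing per arm leave 21/124 vs 36/124, p = 0.024; 6 give 24/127 vs 36/127, p = 0.076; 12 give 30/133 vs 36/133, p = 0.39.

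**4. Restoring deleted cases to a borderline result.**

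- 22/121 vs 36/121, p = 0.035. Two NIV cases restored: 24/123 vs 36/121, p = 0.063. Two restored to each arm: 24/123 vs 38/123, p = 0.040.
- 24/121 vs 36/121, p = 0.074. Two control cases restored: 24/121 vs 38/123, p = 0.047.

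**The case against.** **The deletion may be proper.** The bullets refer to criteria for premature discontinuation which, like the consent pages, are not in the supplied text. If withdrawal of consent there means refusing use of data, leaving the data out respects that refusal. This stands. What would then remain is reporting refusals by arm and the missing robustness analysis.

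**Few patients are affected.** This also stands. A reader might infer that patients who cannot tolerate the mask drop out of the analysis. The documents do not support that: intolerance with early end of sessions is a secondary endpoint, and the exploratory subgroup analyses study premature discontinuation of NIV. Stopping NIV is not withdrawing consent. For an observed ARF to be lost, the patient must have ARF and then formally withdraw.

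**The numbers are small or chosen.** Largely fair. The 9.1% needs 10% of the NIV arm to withdraw consent, none of the controls, doubled risk and the harsher of the two conventions. It also spends that arm's whole non-evaluable allowance on one cause. The tipping table covers missing ARF from any cause, not only deletion under this rule. The borderline results were placed near p = 0.05 and show sensitivity there, not a likely outcome.

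**Missing data are already addressed.** Only in part. The planned analysis of missing data describes their amount and pattern and should be credited, but it names no test of the treatment effect.

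**A further inference to avoid.** The selection section also requires that patients present "no exclusion criteria" in substance, and reoperation during follow-up is listed among those criteria. A reader might infer that reoperated patients are removed after randomisation. The bracket in that criterion reads as barring a second inclusion, so the inference is not supported.

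**Conclusion.** The point holds in a limited form. Section E contains two statements of the intention-to-treat population that disagree on patients who withdraw consent. One of them deletes observed ARF outcomes without separating stopping participation from refusing data use. No planned analysis tests the treatment effect against missing or deleted ARF.

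The bias is probably small. With NIV-arm-only withdrawal at doubled risk, type I error rises by less than 0.1 point at 2% withdrawn and by less than 1 point at 5%. Its direction is unknown. A reader might infer that the rule systematically favours NIV, or that the trial's error rate is near 9%; neither follows from the documents, which give no withdrawal rate and no reason for withdrawal. The planned result would survive all but a strongly unequal distribution of missing cases. The rule matters for a borderline result, which it could move either way.

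These conclusions rest on the assumed withdrawal rates and risk ratios, and on the unsupplied sections not defining withdrawal as refusal of data use. The point is worth fixing because the change is cheap, not because the expected harm is large.

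**What to change.** - In Selection of patients for analysis, keep data collected up to withdrawal in the intention-to-treat analysis unless the patient refuses their use. Report withdrawals and refusals by arm.
- Use one intention-to-treat definition there and in Description of planned statistical methods.
- Beside the planned description of missing data, add one tipping-point table for missing ARF status as a sensitivity analysis, in the form shown above.

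The cost is SAP wording and one table, with no extra patients or visits. Consent wording changes only if the consent and discontinuation sections do not already separate stopping participation from refusing data use. The downside is a little more analysis work and possibly a slightly less favourable estimate. The change should be made before the data are analysed, so that it counts as prespecified.
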